## 4.0 TRIAL DESIGN

### 4.1 Overall Trial Design

This is a Phase 2, randomised, open-label, parallel-group, multicentre trial in which the investigational product, MC2-01 cream, and CAL/BDP ointment (comparator) are investigated in subjects with clinically diagnosed extensive psoriasis vulgaris.

After having provided written informed consent, the subject will undergo screening procedures. Subjects who meet the trial entry criteria will be randomly assigned in a 1:1 ratio to receive either MC2-01 cream or the comparator, CAL/BDP ointment. Subjects assigned to MC2-01 cream will apply 1 dose of trial medication topically once daily for 8 weeks and the subjects assigned to the comparator will apply 1 dose of trial medication topically once daily for 4 weeks.

Please refer to [Figure 4-1](#) for an overview of the trial design for subjects assigned to the MC2-01 cream and refer to [Figure 4-2](#) for an overview of the trial design for subjects assigned to the active comparator.

Trial subjects will be enrolled at approximately 10-15 sites in US.

[figure not shown]
At Week 4, the pharmacokinetic (PK) profile of calcipotriene (CAL), betamethasone dipropionate (BDP) and their main metabolites MC1080 and betamethasone 17-propionate, respectively, will be assessed for both treatment groups. At Week 8, the PK profile of CAL, BDP and their main metabolites will be assessed for the MC2-01 cream treatment group only. At Week 4 and Week 8, the effect of once-daily use of MC2-01 cream on the HPA axis and calcium metabolism will be evaluated for MC2-01 cream treatment group. Other safety assessments (local skin reactions, AEs, laboratory tests, electrocardiogram (ECG)), vital signs and physical examinations) and efficacy assessments are also performed.

The maximum trial duration for each subject will be approximately 12 or 16 weeks and includes a screening period of up to 4 weeks (if washout of medication is required), a treatment period of 4 or 8 weeks, and a follow-up period of up to 4 weeks (if required for follow-up of adverse events, calcium concentrations, and/or HPA axis suppression).

During the trial, the effect of once-daily use of MC2-01 cream on the HPA axis and calcium metabolism will be evaluated for subjects assigned to the MC2-01 cream. Systemic exposure will be assessed for both treatment groups at Week 4, and additionally at Week 8 for the subjects

[figure not shown]

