### 9.2 Study Day and Baseline

For purpose of the SAP, Day 1 is defined as the date of first application of study drug, which corresponds to Randomization/Visit 1 of the study protocol. Study day is calculated relative to the date of Day 1.

Baseline is defined as the last available measurement prior to first application of study drug. Change from baseline is defined as the post-baseline value minus the baseline value.

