### 10.4 Study Drug Exposure and Accountability

Subjects will record the date of each trial medication application in the subject diary. The kit number, and corresponding date dispensed and returned will be collected.

The weight of the returned kits will also be collected.

The following parameters of study medication exposure will be summarized by treatment group and by study period, i.e., from day 1 to Week 4 (both groups) and from day 1 to Week 8 (MC2-01 cream group), for the Safety Population:

- Total number of days of exposure to the study drug, defined as the date of last application of study drug during the period minus date of first application plus one. The last application is the in-clinic dosing at Week 4 visit (Day 1 to Week 4 period) and Week 8 visit (Day 1 to Week 8 period).
- Total number of missed doses during each study period per subject diary
- Total number of applications during each study period, defined as the total number of doses required minus total number of doses missed. Total number of required doses is defined as total number of days of exposure minus any days of investigator approved stop (if applicable)
- Total weight of trial medication used (g) during each study period, defined as the summation of amount of drug used for all dispensed kits. Amount of drug used per kit is defined as the difference in weight between the returned and dispensed kits, where weight

of dispensed kits is a unit value. Amount of drug used for sealed and unreturned kits will be assumed to be 0.0 g

- Amount of drug used per week (g/per week), defined as the total amount of drug used divided by total number of days of exposure to the study drug multiplied by 7

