#### **10.8.2.3 Adverse Events**

AE terms will be coded using MedDRA dictionary (version 20.0). A treatment-emergent AE (TEAE) is defined as an AE with a start date on or after the first application to trial medication (Day 1). If relationship to study medication is missing, the event will be conservatively summarized as being related to study drug. If intensity is missing, a separate category of missing intensity will be included in the summary table, and no imputation of severity will be performed. Through the data cleaning process, all attempts will be made to avoid missing values for relationship and severity.

All AEs will be presented in a by-subject listing, detailing the verbatim term given by the investigator, the PT, SOC, whether or not related to Cosyntropin or study procedure, location of AE to treatment area, start date, stop date, intensity, outcome, relationship to study medication (definitely, probably, possibly, and not related), action taken with study medication, action taken to treat the AE, seriousness and criteria for seriousness. For subjects assigned to MC2-01 cream, all TEAEs will be assigned to the Week 1-4 (starting from Day 1 to 28) or post-Week 4 period (starting from Day 29 and after) based on onset dates. Serious AEs and AEs leading to study drug discontinuation will be presented in a separate listing.

An overall summary of AEs will be presented by treatment and by period (MC2-01 group only). The summary will include the total number of events, frequency counts and percentages with:

- Any AE
- Any TEAE
- Any serious TEAE
- Any treatment-related TEAE
- Any TEAE leading to study drug discontinuation

Summaries of the incidence of TEAEs will be displayed by treatment and by period (MC2-01 group only) according to the following:

- All TEAEs by PT in descending order of frequency (the combined frequency of both treatments)
- All TEAEs by SOC, PT, and maximum severity (mild, moderate, or severe)
- All TEAEs by SOC, PT, and maximum relationship (recorded as 'definitely', 'probably', and 'possibly') to the study drug

At each level of summarization, a subject will be counted once if he/she reported one or more events. The severity of TEAEs and relationship to study drug will be summarized in a similar manner. For summaries of relationship to study drug, a subject will be classified according to the closest relationship. For summaries of TEAE severity, a subject will be classified according to the highest severity.

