#### **10.8.2.5 Safety Laboratory Parameters**

Clinical laboratory (hematology, biochemistry and urinalysis) results will be presented in by-subject listings. Abnormal laboratory findings will be flagged and presented in a separate listing.

Absolute values, changes from baseline, and relative changes from baseline (defined as ratio of the post-baseline vs baseline value) will be summarized using descriptive statistics (means, medians, standard deviations, ranges, and coefficient of variations) by treatment and by visit. Shift tables using extended normal ranges (baseline to Week 4 and most extreme post-baseline value up to Week 4 for both arms) will also be provided.

Urine pregnancy test will be presented in a by-subject listing for subjects with childbearing potential.

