Note: Counts reflect numbers of subjects reporting one or more adverse events that map to MedDRA system organ class or preferred term. A subject may be counted once only in each row of the table.

[1] Includes TEAEs with an onset date on or before Week 4 visit.

[2] Includes TEAEs with an onset date after Week 4 visit.

Generated on XX/XX/XX:XXXX by SMYTEAEP / Uses: XXXX / Reference: Data Listings XXXX

*<Programming Note: sort by SOC in alphabetical order and PT in descending order of the combined frequency in the two active treatments>*

Table 14.3.1.3: Summary of Treatment-emergent Adverse Events  
by System Organ Class, Preferred Term, and Maximum Severity  
Safety Population

System Organ Class Preferred Term	Severity	Weeks 1 – 4 [1]		Post Week 4 [2] MC2-01 Cream (N=XX)
		MC2-01 Cream (N=XX)	Active Comparator (N=XX)	
Subjects with any TEAE, n (%)	Severe	XX (XX.X)	XX (XX.X)	XX (XX.X)
	Moderate	XX (XX.X)	XX (XX.X)	XX (XX.X)
	Mild	XX (XX.X)	XX (XX.X)	XX (XX.X)
		XX (XX.X)	XX (XX.X)	XX (XX.X)
<< Adverse Event System Organ Class >>	Severe	XX (XX.X)	XX (XX.X)	XX (XX.X)
	Moderate	XX (XX.X)	XX (XX.X)	XX (XX.X)
	Mild	XX (XX.X)	XX (XX.X)	XX (XX.X)
<< Adverse Event Preferred Term >>	Severe	XX (XX.X)	XX (XX.X)	XX (XX.X)
	Moderate	XX (XX.X)	XX (XX.X)	XX (XX.X)
	Mild	XX (XX.X)	XX (XX.X)	XX (XX.X)

Note: Counts reflect numbers of subjects reporting one or more adverse events that map to MedDRA system organ class or preferred term. A subject may be counted only once at the highest severity. AEs are categorized by onset date.

Generated on XX/XX/XX:XXXX by XXXXX / Uses: XXXX / Reference: Data Listings XXXX

Table 14.3.1.4: Summary of Treatment-emergent Adverse Events  
by System Organ Class, Preferred Term, and Maximum Causality  
Safety Population

System Organ Class Preferred Term	Causality Assessment[1]	Weeks 1 – 4 [1]		Post Week 4 [2] MC2-01 Cream (N=XX)
		MC2-01 Cream (N=XX)	Active Comparator (N=XX)	
Subjects with any TEAE, n (%)	Related	XX (XX.X)	XX (XX.X)	XX (XX.X)
	Not Related	XX (XX.X)	XX (XX.X)	XX (XX.X)
<< Adverse Event System Organ Class >>	Related	XX (XX.X)	XX (XX.X)	XX (XX.X)
	Not Related	XX (XX.X)	XX (XX.X)	XX (XX.X)
<< Adverse Event Preferred Term >>	Related	XX (XX.X)	XX (XX.X)	XX (XX.X)
	Not Related	XX (XX.X)	XX (XX.X)	XX (XX.X)

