All Randomized Subjects  
[MC2-01 Cream][Active Comparator]

Subject Number	Visit	Visit Date (Day) [1]	Q1	Q2	Q3	Q4	Q5	Q6	Total Score of Q1-Q5
XX-XXX	Visit 3/Week 4	DDMMYY(XX)	XX						
XX-XXX	Unscheduled	DDMMYY(XX)	XX						

Q1 = How easy was the treatment to apply to the skin?; Q2 = How greasy was the treatment when applying it to the skin?; Q3 = How moisturized did your skin feel after applying the treatment?; Q4 = How greasy did your skin feel after applying the treatment?; Q5 = How much did treating your skin disrupt your daily routine?; Q6 = Overall, how satisfied were you with the medical treatment?

[1] Study day is calculated relative to date of first application of study drug (Day 1).

Generated on XX/XX/XX:XXXX by XXXXX / Uses: XXXX

MC2 Therapeutics  
Protocol Number: MC2-01-C3

Page X of Y

Data Listing 16.2.6.7: ACTH Challenge  
All Randomized Subjects  
[MC2-01 Cream][Active Comparator]

Subject Number	Visit	Date (Day) [1]	Cosyntropin Injection Time	Pre-Stimulation		30 Min Post-Stimulation		HPA-Axis Suppression
				Collection Time	Cortisol Level (µg/dL)	Collection Time	Cortisol Level (µg/dL)	
XX-XXX	Visit 1/Day 1	DDMMYY (XX)	HH:MM	HH:MM	XX.X	HH:MM	XX.X	No
	Visit 3/Week 4	DDMMYY (XX)	HH:MM	HH:MM	XX.X	HH:MM	XX.X	No
	Visit 4/Week 8	DDMMYY (XX)	HH:MM	HH:MM	XX.X	HH:MM	XX.X	Yes

[1] Study day is calculated relative to date of first application of study drug (Day 1).

Data Listing 16.2.7.1: Adverse Events  
All Randomized Subjects  
[MC2-01 Cream][Active Comparator]

Subject Number	AE #	MedDRA SOC Term/ MedDRA Preferred Term / (Verbatim Term)	TEAE? [1] / Period Onset Date (Day) – End Date (Day) [2]	Related to Cosyntropin?/ Related to Study Procedure?	Outcome/ Withdraw due to AE?	SAE: Criteria?/ Severity	Location to Treatment Area/ Relationship to Study Medication	Action Taken / Other Action Taken
XX-XXX	1	XXXXXXXX / XXXXXXXX / (XXXXXXXX)	Yes / 1 DDMMYYYY(XX) – DDMMYYYY(XX)	No/No	XXXXXXXX/ Yes	Yes: Hospitalization / Mild	Inside treatment area/ Definitely Related	XXXXXXXX / XXXXXXXX
	2	XXXXXXXX / XXXXXXXX / (XXXXXXXX)	No / NA DDMMYYYY(XX) – Ongoing	No/Yes	XXXXXXXX/ No	No/ XXXXXXXX	Outside treatment area/ XXXXXXXX	XXXXXXXX / XXXXXXXX
XX-XXX	1	XXXXXXXX / XXXXXXXX / (XXXXXXXX)	Yes / 2 DDMMYYYY(XX) – DDMMYYYY(XX)	No/No	XXXXXXXX/ XX	No/ XXXXXXXX	Non-cutaneous/ XXXXXXXX	XXXXXXXX / XXXXXXXX

Period 1=Week 1-4; Period 2=Post Week4.

[1] A treatment-emergent AE (TEAE) is defined as an AE with a start date on or after the first application to trial medication.

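### The SAP gives two incompatible rules for the Weeks 1-4 adverse event period, and it ends laboratory shift tables at Week 4 without recording the departure from the protocol

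*SAP*

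**What the plan says.** **Adverse event period.** SAP 10.8.2.3 states that, for cream subjects, "all TEAEs will be assigned to the Week 1-4 (starting from Day 1 to 28) or post-Week 4 period", with Day 29 opening the second period. It restricts the split by period to the cream group and gives no cut-off for the comparator.

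The Table 14.3.1.2 shell has a Weeks 1-4 heading over both arms and a Post Week 4 column for cream only. Its note [1] reads "Includes TEAEs with an onset date on or before Week 4 visit" and its note [2] reads "Includes TEAEs with an onset date after Week 4 visit". Tables 14.3.1.1, 14.3.1.3 and 14.3.1.4 carry the same [1] and [2] markers with no definition of the period, and 14.3.1.4 also uses [1] for causality. The adverse event listing gives only "Period 1=Week 1-4; Period 2=Post Week4".

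Two other SAP definitions bear on this. Section 9.2 fixes the day count: "Day 1 is defined as the date of first application of study drug, which corresponds to Randomization/Visit 1 of the study protocol". Section 10.4 ends the four-week exposure period at the visit: "The last application is the in-clinic dosing at Week 4 visit (Day 1 to Week 4 period").

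**Laboratory shifts.** Protocol 8.8.4 plans shifts from baseline to the most extreme value after baseline, without a time limit. Protocol 8.8 wants the number of out-of-range laboratory values shown separately for Weeks 1 to 4 and Weeks 5 to 8. SAP 10.8.2.5 limits the shift tables to Week 4 itself and the "most extreme post-baseline value up to Week 4 for both arms", and the Table 14.3.2.2.X shell does the same. SAP section 11, which lists changes from the protocol, covers only the criterion for HPA suppression.

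**The concern.** A programmer who follows the SAP text and one who follows the table note will produce different adverse event tables, and the SAP does not say which prevails.

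The day on which the rules part is not an empty one. In the cream arm, the Week 4 visit includes the ACTH challenge, an ECG, laboratory tests, a physical examination and serial PK sampling (Protocol Table 7-2). New clinically significant ECG findings are reported as adverse events (Protocol 7.10), and the event listing records any relation to cosyntropin or to study procedures. Onsets on that day are therefore plausible. If the text is followed, an event on a Day 29 visit counts as Post Week 4 for cream but as Weeks 1-4 for the comparator, in columns meant to be read side by side.

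For the laboratory data, the missing part is Weeks 5 to 8. That is the stretch of cream treatment that goes beyond the comparator's four weeks, and so the part for which the shift table has most to add.

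**Working it through.** The plan gives no figure to reproduce. The check is day arithmetic and a comparison of sections.

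**1. Put the Week 4 visit on the SAP's day count.**
- Visit window in both arms: protocol Day 28 ± 2, that is Day 26 to 30 (Protocol Tables 7-2 and 7-3).
- SAP Day 1 = protocol Day 0 (SAP 9.2), so SAP day = protocol day + 1.
- The Week 4 visit is therefore nominally SAP Day 29, with range 27 to 31.

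**2. Compare the two rules for cream subjects.** The text window is 28 days. A window that ends at the visit has as many days as the SAP day of the visit.

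| Visit, SAP day | Text window minus visit window (days) | Relative difference | Onset days classified differently |
|---|---|---|---|
| 27 | 28 − 27 = +1 | 1/27 = +3.7% | 28 |
| 28 | 28 − 28 = 0 | 0% | none |
| 29 (nominal) | 28 − 29 = −1 | 1/29 = −3.4% | 29 |
| 30 | 28 − 30 = −2 | 2/30 = −6.7% | 29, 30 |
| 31 | 28 − 31 = −3 | 3/31 = −9.7% | 29, 30, 31 |

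The rules agree only for a visit on SAP Day 28. They disagree on 4 of the 5 allowed days. On 3 of the 5 (Days 29, 30 and 31) the text places the visit day itself after Week 4. The percentages describe calendar time, not event counts.

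**3. Follow a comparator event through each rule.** Events are collected until the end of the study (Protocol 7.13.1), and Protocol 4.1 allows "a follow-up period of up to 4 weeks (if required for follow-up of adverse events" and other reasons).
- Text rule: the comparator is not cut, so an event after the Week 4 visit goes into its only column, Weeks 1-4.
- Note rule: the same event is excluded from Weeks 1-4, and the comparator has no later column to receive it.

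**4. Check the laboratory tables.** Cream subjects have haematology and biochemistry at Week 8, and a repeat calcium test at Week 6 if the Week 4 value is above range (Protocol 7.9.1).
- Shift panels in Table 14.3.2.2.X: Week 4, and most extreme value up to Week 4.
- Shift panels that use data after Week 4: 0.
- Planned cream subjects affected: 60/2 = about 30 randomised.

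The two existing panels are not duplicates, because early termination tests (Protocol 7.16) and unscheduled visits (Protocol 7.14) can feed the second. Week 8 values do appear in Tables 14.2.5 and 14.3.2.1.X, but as means and quantiles, and in Listing 16.2.8.3, but as rows. No planned haematology or biochemistry table counts cream subjects who move out of range after Week 4.

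**The case against.** The text rule can be defended in its own right. Days 1 to 28 are exactly four weeks in the SAP's count, so a cut at Day 28/29 is a literal reading of the protocol's Weeks 1 to 4 and Weeks 5 to 8. Nothing requires the adverse event period to match the exposure period. A fixed cut in both arms would also give equal windows, whereas a visit-based cut gives windows of 27 to 31 days.

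The conflicting note stands under one shell only, in a section that outlines proposed tables. The listing header that names both arms is generic, so it is weak evidence of a comparator split. Comparator follow-up takes place only for unresolved events, whose onset comes before the visit, so few new comparator onsets would be seen afterwards.

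On the laboratory side, the protocol calls its statistics an overview to be detailed in the SAP. Its request by period concerns out-of-range values rather than shifts. The missing item is a single descriptive cross-tabulation.

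Most of this stands as a limit on weight. It does not remove either fact: the two adverse event rules differ, and the Week 4 limit on shifts is unrecorded. The defence of a fixed cut also fails for the plan as written, because the text applies it to one arm only.

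**Conclusion.** Both parts hold. The adverse event rules disagree on 4 of 5 allowed visit days, by 1 to 3 onset days and including the on-schedule visit, and neither rule treats late comparator events coherently. The laboratory shift tables drop everything after Week 4 in the cream arm, and section 11 is silent about it.

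The harm is limited. The adverse event and shift tables are descriptive, and no PK comparison, HPA summary or calcium summary depends on them. The Week 4 shift panels are valid for comparing the arms. The effect on event counts is likely to be small and could go either way, but it cannot be sized from the documents. The figure of about 30 is planned randomised cream subjects; the number with Week 8 tests will be lower if any drop out. The point should be corrected before programming, because the SAP as it stands supports two different safety tables.

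**What to change.** **Adverse events.** In SAP 10.8.2.3, all four adverse event shells and the adverse event listings, define Weeks 1-4 as onset on or before the actual Week 4 visit date, in both arms. State a fallback for subjects without that visit, for example SAP Day 29, the nominal day. Give later comparator events a Post Week 4 column or row. Define the markers under every table, and use a different one for causality in 14.3.1.4. A fixed Day 28 cut in both arms would also remove the contradiction; the visit-based rule is preferred because it matches the existing note and the exposure period in 10.4.

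**Laboratory shifts.** Keep both Week 4 panels for the two-arm comparison. Add cream panels to Table 14.3.2.2.X for baseline to Week 8 and for baseline to the most extreme value over the whole study, with albumin-corrected calcium among the parameters. If these are not added, record and justify the Week 4 limit in section 11.

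**Cost.** Wording and shell edits only, with slightly more table output. The cream Weeks 1-4 event count may move slightly in either direction.

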#### **10.8.2.4 Local Skin Reaction (LSR) Assessment**

LSR assessments by investigator and subject will be summarized using frequency counts and percentages by treatment and visit. By-subject listings will be provided.

#### **10.8.2.5 Safety Laboratory Parameters**

Clinical laboratory (hematology, biochemistry and urinalysis) results will be presented in by-subject listings. Abnormal laboratory findings will be flagged and presented in a separate listing.

Absolute values, changes from baseline, and relative changes from baseline (defined as ratio of the post-baseline vs baseline value) will be summarized using descriptive statistics (means, medians, standard deviations, ranges, and coefficient of variations) by treatment and by visit. Shift tables using extended normal ranges (baseline to Week 4 and most extreme post-baseline value up to Week 4 for both arms) will also be provided.

Urine pregnancy test will be presented in a by-subject listing for subjects with childbearing potential.

#### 10.8.2.6 Vital Signs

Vital signs data will be presented in a by-subject listing. Observed values and changes from baseline will be summarized using descriptive statistics by treatment and visit.

#### 10.8.2.7 Electrocardiograms (ECG)

ECG data will be presented in a by-subject listing, with flagging of abnormal results.

#### 10.8.3 Physical Examination (PE)

Physical examination results will be present in a by-subject listing.

### 10.9 Pharmacokinetics Analysis

All analyses of pharmacokinetics (PK) will be based on the PK population.

All available concentration results will be summarised using appropriate descriptive statistics (number of subjects, number of quantifiable concentrations, median, lower and upper quartiles, minimum, maximum) for active ingredients (BDP and CAL) and for their major metabolites. A listing for sample date/times as well as derived sampling time deviations will be provided. Median and individual concentration versus time curves will be plotted (linear and semi-log plots). Nominal sample collection times will be used in determining concentration descriptive statistics and plotting median concentration versus time profiles.

All analyte concentrations below the lower limit of quantification (BLOQ) will be reported as the lower limit of quantification (LLOQ) and will be treated as LLOQ in descriptive statistics and plasma concentration-time profiles.

